## **6.6.2** Ocular Alignment

The proportion of participants with development of new strabismus by cover testing at distance or near (no heterotropia at baseline and the presence of near and/or distance heterotropia at a subsequent visit) or an increase from baseline  $\geq 10\Delta$  by PACT in a pre-existing strabismus at any time on randomized treatment during the study will be reported by treatment group and compared using Barnard's exact test.

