Primary Endpoint	
 
The primary efficacy endpoint will be mean change in amblyopic eye logMAR distance VA between randomization and VA at completion of randomized treatment or at 56 weeks, whichever is earlier.
 
The primary endpoint for each participant is defined as:
 
1. Amblyopic eye VA (calculated as mean of test and retest) at the last visit that was the basis for a "stable resolved" or "stable residual" determination (in the sequential group, stable residual amblyopia criteria can be reached only after patching has been instituted); or
 
2. Amblyopic-eye VA at 56 weeks (calculated as mean of test and retest) in those completing a 56 week visit without ever meeting criteria for "stable resolved" or "stable residual" amblyopia (if retest missing at 56 weeks, the single test value will be used).
 
To determine if the following endpoints differ between simultaneous treatment and sequential
 

Secondary Objectives/Endpoints	treatment groups.  Efficacy:  Child and parental health-related quality of life (HRQOL) domain scores as measured by PedEyeQ.  Proportion of participants with improvement of amblyopic eye distance VA of 2 or more logMAR lines (>=10 letters if E-ETDRS), using the primary endpoint as defined above.  Time to stable resolved amblyopia.  Amblyopic-eye distance VA (calculated as mean of test and retest) after 8 weeks.  Amblyopic-eye distance VA (calculated as mean of test and retest) at 56 weeks for all participants.  Binocularity by Randot Preschool Stereotest, Randot Butterfly Stereotest, and Worth 4 Shape Testing.  Monocular contrast sensitivity.  Safety:  Worsening of best-corrected fellow-eye distance VA of 0.2 logMAR lines or more at any time during the study from baseline (based on mean of test and retest, or initial test if retest not done).  Proportion of participants who develop a new strabismus.

	Proportion of participants who develop mild moderate and severe skin imitation from
	
 
Proportion of participants who develop mild, moderate, and severe skin irritation from patching.
 

	To evaluate the following endpoint within simultaneous treatment and sequential treatment groups:
	Recurrence of amblyopia in those who have resolved (defined as a 0.2 or more logMAR reduction and IOD of 0.2 logMAR or more from value at visit of resolution).

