#### Eligibility Criteria:

258 259

- 1. Age 3 to <13 years at the time of randomization
- 2. Amblyopia associated with anisometropia, strabismus, or both
  - o Criteria for strabismic amblyopia: At least one of the following must be met:
    - Presence of a heterotropia on examination at distance or near fixation (with or without optical correction)
    - Documented history of strabismus which is no longer present (which in the judgment of the investigator could have caused amblyopia)
  - o Criteria for anisometropia: At least one of the following criteria must be met:
    - ≥1.00 D difference between eyes in spherical equivalent (SE)
    - ≥1.50 D difference in astigmatism between corresponding meridians in the two
  - o Criteria for combined-mechanism amblyopia: Both of the following criteria must be
    - Criteria for strabismus are met (see above)
    - ≥1.00 D difference between eyes in spherical equivalent OR ≥1.50 D difference in astigmatism between corresponding meridians in the two eyes
- 3. No previous treatment for amblyopia, including total spectacle wear as specified below:
  - a. No more than 72 hours of spectacle wear if spectacle wear attempted more than 3 months prior to the Enrollment Visit
  - b. No more than 24 hours of spectacle wear if spectacle wear attempted less than 3 months prior to the Enrollment Visit.

- 4. Investigator planning to initiate (or has already prescribed) spectacle correction of refractive error meeting the following criteria based on a cycloplegic refraction that has been performed within 45 days of the Enrollment visit **and** within 90 days of the Spectacle Baseline visit:
  - a. Full correction of spherical and cylindrical anisometropia.
  - b. Full correction of astigmatism with the same axis found by the cycloplegic refraction.
  - c. Allow symmetric reduction of sphere up to 1.50, prescribing such that the most hyperopic meridian is not rendered myopic, in the non-amblyopic eye at baseline.
  - d. Allow symmetric addition of only -0.25 sphere for participants with plano sphere, spherical myopia, simple or compound myopic astigmatism in the non-amblyopic eye at baseline.

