## 4. Ocular Alignment Testing:

• Ocular alignment will be assessed in current spectacle correction by the cover test, simultaneous prism and cover test (SPCT) (in cases of strabismus detected by cover test), and prism and alternate cover test (PACT) in primary gaze at distance (3 meters) and at near (1/3 meter).

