843	Patching could potentially decrease the VA in the sound eye, although this is almost always
844	reversible and extremely unlikely when the sound eye has several hours without occlusion each
845	day. The diagnosis and management of reverse amblyopia is left to the Investigator's judgment.
846	
847	Patching could precipitate the development of an ocular deviation (strabismus), although this has
848	been found to be very rare in our previous studies and indistinguishable from the natural history
849	of amblyopia. If treatment precipitates the development of an ocular deviation (e.g., esotropia in
850	participants with hyperopia), the parent will be advised to have the child see the investigator as
851	soon as possible.
852	

853	5.5 Reporting of Adverse Events
854	No surgical procedures are part of the protocol. There are no expected long-term adverse events
855	associated with spectacles or patching. Investigators will abide by local IRB reporting
856	requirements.
057	•

857858

859

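### Section 6.6.2 counts returning strabismus as new and compares arms over an on-treatment window that is longer by design for sequential children who need patching

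*Protocol*

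**What the plan says.** Section 6.6.2 pools two events in one proportion. The first is new strabismus: "no heterotropia at baseline and the presence of near and/or distance heterotropia at a" subsequent visit. The second is an increase of at least 10 prism dioptres "by PACT in a pre-existing strabismus at any" time. Both count only at a "time on randomized treatment during the study will be reported by treatment group and" the two proportions are "compared using Barnard's exact test", with no adjustment for time observed.

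Three other places bear on this.

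- **Eligibility (section 2.3, criterion 2)** accepts as strabismic amblyopia a heterotropia seen with or without correction. It also accepts a "Documented history of strabismus which is no longer present".
- **Baseline testing (section 3.1.3, item 4):** "Ocular alignment will be assessed in current spectacle correction by the cover test" and prism tests, that is, in the new spectacles.
- **End of randomized treatment (sections 4.3.2 and 6.4).** A patched child in either arm is released to investigator discretion at non-improvement. In the sequential arm a stable residual outcome is possible only once patching has begun.

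The Protocol Summary names the safety endpoint simply as "Proportion of participants who develop a new strabismus", with no on-treatment limit and no worsening component. Section 5.4.2 says that strabismus precipitated by patching has "been found to be very rare in our previous studies and indistinguishable from the natural history" of amblyopia.

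**The concern.** Two features weaken the comparison, in different ways.

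**Label.** A child enrolled because of strabismus, but straight in spectacles on day 0, is at risk of becoming a new case. If the known deviation returns, that is reappearance, not onset. The threshold is also uneven: any heterotropia counts for this child, while a child with a deviation at baseline needs a 10-prism-dioptre increase.

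**Window.** Observation stops when randomized treatment stops, and the arms stop at different times by design. If background events cannot be told from treatment-related ones, as section 5.4.2 says, they accumulate with time observed, and the arm watched longer collects more.

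Section 6.6 says that type II error matters more than type I error in safety analyses. Dilution is a type II problem. A window that adds background events to the sequential arm can hide a harm of earlier patching or make spectacles-first look worse.

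**Working it through.** **The plan's own figures.** The protocol states no rate or power for strabismus. The only relevant figure is 136 per arm (section 6.12.4). For two one-sided tests at a true difference of 0, n = 2 × 1.7² × (1.960 + 1.645)² / 0.75² ≈ 134 per arm. With the t correction, 136 per arm gives power 0.904. The figure reproduces and serves below only as the sample size.

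**Share of the sequential arm on the longer path.** From Table 1 (section 6.12.1.1), 46 + 55 = 101 children had residual amblyopia after spectacles. That is 101/139 = 73% of those enrolled and 101/129 = 78% of those who finished the spectacle phase.

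**Earliest exit.** Classification starts at the 8-week visit. A simultaneous child with residual amblyopia can be stable there: one interval. A sequential child with residual amblyopia must plateau on spectacles, start patching and plateau again: two intervals, 16 weeks.

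**Effect of the window.** Let h be the event probability per 8-week interval off patching, k·h the probability while patching, and q the share going on to patching. On the shortest paths:

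- simultaneous = k·h
- sequential = (1 − q)·h + q·[1 − (1 − h)(1 − k·h)]

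With q = 0.783 and an assumed h = 2%:

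- k = 1: 0.0200 against 0.217 × 0.02 + 0.783 × 0.0396 = 0.0353, ratio 0.57
- k = 2: 0.0400 against 0.217 × 0.02 + 0.783 × 0.0592 = 0.0507, ratio 0.79

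Other pathways, with h from 1% to 4%:

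| Intervals on randomized treatment | k = 1 | k = 2 | k = 3 |
|---|---|---|---|
| Sim 1; seq 1 spectacles + 1 patching | 0.56–0.57 | 0.78–0.80 | 0.90–0.92 |
| Sim 2; seq 2 + 2 | 0.57–0.58 | 0.79–0.81 | 0.91–0.94 |
| Sim 2; seq 2 + 1 | 0.72–0.73 | 1.12–1.13 | 1.37–1.38 |
| Sim 3; seq 2 + 2 | 0.84–0.85 | 1.17 | 1.32–1.34 |

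Under no effect the ratio is below 1 in every row. The true ratio of hazards is k.

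*Sensitivity to q.* Section 1.2 expects at least 25–40% to resolve with spectacles. With q = 0.60, shortest paths and h = 2%, the ratios are 0.020/0.0318 = 0.63 (k = 1) and 0.040/0.0435 = 0.92 (k = 2).

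**Absolute size.** For k = 1 on the shortest paths the spurious excess is 136 × q × h(1 − h). With q = 0.783:

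| h per 8 weeks | Implied 56-week risk, 1 − (1 − h)⁷ | Excess sequential cases |
|---|---|---|
| 0.2% | 1.4% | 0.2 |
| 1% | 6.8% | 1.1 |
| 2% | 13.2% | 2.1 |
| 4% | 24.9% | 4.1 |

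**Common windows, same model.** To 8 weeks the ratio equals k, because no sequential child has yet had protocol patching. To 56 weeks it is 1.00 for k = 1 and 1.02 to 1.16 for k = 2.

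**Dilution from prior strabismus.** Assume true risks of 6% and 2%, a share s with prior strabismus, and reappearance r equal in both arms over a common window. Observed risk = (1 − s) × true + s × r. With s = 10% and r = 40%: 0.054 + 0.040 = 9.4% against 0.018 + 0.040 = 5.8%. The ratio falls from 3.0 to 1.6, and power at 136 per arm from 0.39 to 0.20 (normal approximation). Over s = 5–30% and r = 20–60% the ratio runs from 2.3 down to 1.1 and power from 0.31 to 0.08.

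**The case against.** A reader might infer that the endpoint cannot show whether early patching causes strabismus. The protocol does not support that. Its stated comparison is between two strategies, both of which may include patching, and a large effect could still appear: at k = 3 the ratio reaches 1.38 on some paths.

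A reader might also take the mislabelling for bias. Randomization balances children with prior strabismus in expectation, so it costs sensitivity. Since section 6.6.2 already pools worsening of existing strabismus, a returning deviation arguably belongs in a general alignment-deterioration count. What remains is the label and the lack of a breakdown.

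The strongest objection is to size. Section 5.4.2 says very rare and gives no rate, and at low rates the artefact is a fraction of a child. A constant hazard is also assumed; if deviations cluster early, the extra weeks add little. Nor does section 6.6.2 say when randomized treatment ends for stable resolved children, who stay in spectacles to 56 weeks. If they stay in the window, the gap concerns only children with residual amblyopia. All of this stands and limits the magnitude. It does not remove the unequal exit for residual children or, under equal hazards, its direction.

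An on-treatment window is conventional, section 6.6.1 uses one too, and the data monitoring committee can request other comparisons. That is a reason to keep the on-treatment count, not to make it the only comparison. The shorter Summary wording is better read as shorthand than as a contradiction.

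Finally, a 56-week window alone is no cure: it is nearly insensitive to a doubled hazard and includes treatment at investigator discretion and strabismus surgery permitted after release (section 5.3).

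**Conclusion.** The point holds in limited form and should be corrected. Section 6.6.2 mixes reappearance of known strabismus with new onset, which dilutes the comparison. It also compares crude proportions over a window that is longer by design for sequential children who need patching. With equal hazards, the expected simultaneous/sequential ratio is about 0.56 to 0.85 on the pathways examined. A doubling of hazard under patching could appear as anything from 0.78 to 1.17, so a harm of earlier patching may be masked or reversed.

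The direction under equal hazards follows from the design. The size rests on an assumed constant hazard, assumed pathway lengths, q taken from an earlier study with different visit intervals and a different definition of resolution, and the on-treatment window ending at the outcome visit. In absolute terms it may be under one or two children per arm.

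**What to change.** In section 6.6.2:

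1. Report three components separately: truly new strabismus, among children who met no strabismus criterion at eligibility; reappearance in children with past or spectacle-controlled strabismus; and the 10-prism-dioptre increase in pre-existing strabismus.
2. Compare arms over common windows: cumulative to the 8-week visit, before protocol patching can start in the sequential arm, and cumulative to 56 weeks; or by time to event.
3. Keep the on-treatment proportion as supportive, and state when randomized treatment ends for stable resolved children.

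The cost is wording and programming. Alignment is already tested at every visit to 56 weeks, and type of amblyopia is already a subgroup in section 6.11. The downsides are few events by 8 weeks, and 56-week events that may reflect discretionary treatment or surgery after release; these should be flagged in the table.

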#### 1101 6.6.3 Skin Irritation from Patching 1102 The proportion of participants with skin irritation from patching reported as "severe" at any time 1103 during the study, using the severe, moderate, or mild scale, will be tabulated for each randomized 1104 treatment group. 1105 1106 **Adherence with Randomized Treatment** 1107 1108 Adherence with Spectacles 1109 Data from the parental calendar of spectacle wear will be used to calculate a subjective measure 1110 of adherence. The average % of spectacle treatment completed across visits will be defined by the investigator as poor (<25%), fair (25% to <50%), good (50% to <75%), or excellent 1111 (>=75%), based on investigator impression of the total hours of spectacle wear since the last 1112 1113 study visit. 1114 1115 Adherence with Patching 1116 Data from the occlusion dose monitor (ODM) will be used to calculate an objective measure of 1117 adherence. The proportion of patching completed will be defined as the total hours of patching 1118 divided by the total hours of prescribed patching over a specified period of time. 1119 1120 6.7.1 Adherence within the Sequential Treatment Group 1121 1122 **6.7.1.1** While Wearing Spectacles Alone 1123 The adherence with spectacles between randomization and the visit at which VA stability or 1124 resolution with spectacles alone was achieved will be calculated as described in section 6.7 for 1125 each participant and the distribution within those randomized to sequential treatment will be 1126 summarized. 1127 1128 Average adherence with spectacle wear over the total number of study visits will be 1129 dichotomized based on having excellent (an average of 3 or higher) adherence, and the mean improvement in amblyopic eye VA will be compared between the 2 groups (average adherence 1130 of $\geq 3$ or higher versus average of < 3) thus defined using ANCOVA, with adjustment for baseline 1131 age and amblyopic eye VA. 1132 1133 1134 6.7.1.2 While Wearing Spectacles and Patching After Stable VA on Spectacles Alone 1135 For participants who initiate patching after reaching stable amblyopic eye VA with spectacles 1136 alone, their adherence with patching between the visit at which patching was initiated and the 1137 visit at which a "stable resolved" or "stable residual" determination was made while on 1138 spectacles and patching will be calculated as described in section 6.7 for each participant, and the 1139 distribution within those randomized to sequential treatment will be summarized. 1140

- 1141 A Spearman correlation coefficient and 95% CI for the correlation between adherence with 1142 patching and improvement in amblyopic eye VA while wearing the patch, adjusted for age and
- baseline amblyopic eye VA, will be calculated to assess the strength of the relationship.

1144

Adherence with patching will be dichotomized based on having 80% or higher adherence. The mean improvement in amblyopic eye VA will be compared between the 2 groups (≥80% versus

1147	<80% adherence with patching) using ANCOVA, with adjustment for baseline age and
1148	amblyopic eye VA.

1149 1150

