## 6.6 Safety

The PEDIG DSMC will review safety data tabulated by treatment group at each of its semi-annual meetings and can request formal statistical comparison of any safety outcome at any time if they have cause for concern. As type II error is more of a concern than type I error in safety analyses, we will use p<0.05 without adjustment for multiplicity to define statistical significance in all safety analyses.

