## **6.12.4 Sample Size Estimation**

Based on previous data from ATS5 on sequential treatment (mean improvement of 3.7 logMAR lines) and data from Agervi et al (median improvement of 4 logMAR lines), we propose to design the present study to test whether the two treatments are equivalent, where equivalent is defined as a difference in mean improvement of less than 0.75 logMAR lines.

Assuming that the true difference in mean VA change between the two groups is 0 and assuming a pooled standard deviation of 1.7 logMAR lines, a total sample size of 272 participants (136 per group) has 90% power with a type I error rate of 2.5% to reject the null hypothesis of non-equivalence in favor of the alterative that simultaneous treatment is equivalent to sequential treatment (Table 3).

The percentage of participants lost to follow-up or withdrawn is expected to be small overall (10%) and equal between the two treatment groups. No adjustment to sample size has been made since outcome VA will be imputed for these participants (see *section 6.4*).

Table 3. Total Sample Size Estimates for a 2-Arm Study \*

SD of Change (LogMAR lines)	Treatment Group Difference in Mean VA Change from Baseline (logMAR lines) Equivalence Margin			
	<0.50	<0.75		
1.6	538	242		
1.7	606	272		
1.8	678	304		
1.9	756	338		

 \* The number of participants in cells represents the total number of participants required to reject a 2-sided null hypothesis that simultaneous treatment is not equivalent to sequential treatment by >=0.75 logMAR lines in favor of the alternative that simultaneous treatment is equivalent to sequential, with an equivalence margin of <0.75 logMAR lines; from 2 one sided T-tests with an alpha=0.025 and power 90% for a range of pooled SD of change in VA (logMAR lines).

A sample size of 272 participants for an equivalence study will have 90% power to reject a null hypothesis of no difference in favor of an alternative superiority hypothesis that there is a

- difference between groups, if the true difference between groups is as small as 0.67 logMAR lines of VA, with a type 1 error rate of 5%.
- 1334

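### The protocol summary lists mild, moderate and severe skin irritation for comparison between arms, but section 6.6.3 tabulates only severe irritation and names no comparison for any grade

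*Protocol*

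**What the plan says.** The Protocol Summary introduces its between-arm list of secondary endpoints, efficacy and safety together, with "To determine if the following endpoints differ between simultaneous treatment and sequential" treatment groups. The third safety entry in that list is "Proportion of participants who develop mild, moderate, and severe skin irritation from patching".

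Section 6.6.3, the analysis section for this endpoint, covers "The proportion of participants with skin irritation from patching reported as 'severe' at any time", and continues "during the study, using the severe, moderate, or mild scale, will be tabulated for each randomized" treatment group. That is the whole of the planned analysis.

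The neighbouring sections go further. Section 6.6.1 compares mean change in fellow-eye acuity by ANCOVA, and compares the proportion losing two or more lines with Barnard's exact test. In section 6.6.2 the proportion with new or increased strabismus "will be reported by treatment group and compared using Barnard's exact test".

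Section 6.6 sets the frame for all three. It ranks type II error above type I error as a concern for safety, and so "we will use p<0.05 without adjustment for multiplicity to define statistical significance". It adds that the DSMC sees safety data by arm twice a year and "can request formal statistical comparison of any safety outcome at any time" if it has cause for concern.

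**The concern.** The endpoint and its analysis do not match in two respects. The first is grade: the summary has three and 6.6.3 has one. The second is purpose: the summary asks whether the arms differ, while 6.6.3 only tabulates.

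An analyst working from 6.6.3 would produce one severe-irritation row per arm. An analyst working from the summary would produce all three grades and a comparison. Both would be following the protocol.

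The endpoint bears on the question the trial asks. Sections 1.3 and 1.9 argue for sequential treatment partly because some children will never need a patch, so patch tolerability by randomized arm is relevant to readers. Section 5.4.2 names skin irritation first among the risks of patching, and what it says there does not depend on grade. Limiting the table to the most extreme grade, with no comparison, also sits poorly with the stated priority on type II error in safety analyses.

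**Working it through.** No figure in the protocol bears on this point, so the check is a comparison of the texts.

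1. **Grades.** The summary names mild, moderate and severe. Section 6.6.3 names the same scale as the instrument, then restricts the reported proportion to severe. Mild and moderate have no line in 6.6.3 or elsewhere in section 6.6.
2. **Comparison.** The summary places the endpoint under a heading about differences between arms. Section 6.6.3 gives a tabulation by arm, with no test, no confidence interval and no estimated difference. The stated comparison is therefore missing for severe irritation as well as for the two lower grades.
3. **Sibling endpoints.** Of the three safety endpoints in the summary, fellow-eye acuity loss has a named test in 6.6.1 and new strabismus has one in 6.6.2. Skin irritation alone has none. The protocol does name tests for safety outcomes, so the gap is specific to 6.6.3.
4. **Significance level.** Section 6.6 fixes an unadjusted 0.05 for all safety analyses. For skin irritation that level has no test to attach to.
5. **Possible cover elsewhere.** Section 6.5 says the distributions of all secondary outcomes will be tabulated by group at randomization and at the outcome visit. That sentence stands under the efficacy heading. Even if it extends to safety, a table at two visits would not capture irritation occurring at any time in the study, and it is not a comparison.
6. **Size.** To say how much information is lost, one would need irritation rates by grade and by arm. The protocol gives none. Section 6.12.4 supplies only the denominator for the younger cohort ("a total sample size of 272 participants", 136 per group), and a denominator alone yields no power or event count. The older cohort is analysed separately under section 6.2 and has no fixed size.

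**The case against.** The strongest case against is that this is a matter of wording. The SAP is not at hand, and grade-level safety tables are commonly left to it. The DSMC can ask for a formal comparison whenever it has cause for concern. Section 5.5.1 rates the study as no more than minimal risk. A test may also add little: under section 3.2 every child in the simultaneous arm is assigned patching from randomization, while children in the sequential arm patch only if needed. A difference in any-grade irritation would then largely restate the difference in exposure, and plain tabulation is a defensible choice.

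Part of this stands. Tabulation without a test would be a reasonable plan if the summary said so, and amending the summary would also remove the contradiction. The low risk and the secondary status of the endpoint keep the point modest.

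The rest does not remove it. The protocol has not left the analysis to the SAP: it specifies one, and that analysis disagrees with its own endpoint. A comparison made at the DSMC's discretion is not a prespecified final analysis. The exposure argument bears on whether to test, and gives no reason for leaving two of three grades out of the table.

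**Conclusion.** The inconsistency is real and lies in the current text. Section 6.6.3 delivers neither the three grades nor the between-arm comparison that the summary sets out. It affects one secondary safety endpoint; the primary equivalence analysis, the sample size and the other safety analyses are untouched. No magnitude can be given, because that would rest entirely on assumed event rates.

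A reader might infer more: that most of the harm from patching escapes comparison between arms, or that mild and moderate events are thrown away. The protocol does not support either reading. It gives no distribution of grades, so the share that is mild or moderate is unknown. Section 5.4.2 lists two other risks of patching, reduced acuity in the sound eye and a new ocular deviation, and both have named arm comparisons in 6.6.1 and 6.6.2. Absence from 6.6.3 means there is no planned analysis in the protocol; it does not mean the data are discarded. Nor would 6.6.3 by itself support a claim that irritation does not differ between arms, since it produces no p-value or interval.

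**What to change.** Align 6.6.3 with the summary. Tabulate the worst reported grade per participant (none, mild, moderate, severe) by randomized group, separately within each age cohort as section 6.2 requires. Name the between-group comparison, for example Barnard's exact test at unadjusted p<0.05, as for the binary outcomes in 6.6.1 and 6.6.2. That test needs a two-by-two table, so the text should state which proportion or proportions it applies to. The protocol fixes no cut-point across grades, and the choice is the study team's.

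If the team prefers description only, the summary should be amended to say so, and 6.6.3 should still show all three grades.

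The cost is one paragraph and one table. Section 6.6.3 already refers to the graded scale, so no new visits are needed, and no new data either, provided the grade is recorded on the case report form as that section implies.
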